8.5.2 Incomplete Stop Date and Time

The following rules will be applied to impute the missing numerical fields. If the imputed stop date is before the start date (imputed or non-imputed start date), then the imputed stop date will be equal to the start date.

Missing Day and Month

- If the year of the incomplete stop date is the same as the year of the date of the study discontinuation/completion, the stop day and month will be set to the maximum of the date of study discontinuation/completion, as appropriate, or the date equivalent to 35 days after the last dose of IMP.
- If the year of the incomplete stop date is before the year of the date of study discontinuation/ completion, as appropriate, or the date equivalent to 35 days after the last dose of IMP, the day and month will be set to 31 December.
- If the year of the incomplete stop date is after the year of the date of study discontinuation/ completion, as appropriate, or the date equivalent to 35 days after the last dose of IMP, the day and month will be set to 01 January.

Missing Month Only

• The stop day will be treated as missing and both month and day will be replaced according to the above procedure.

Missing Day Only

• The stop day will be set to the last day of the month.

Totally Missing Stop Date

• The concomitant medication will be considered ongoing.

Missing /Incomplete Time

- If the time is missing, it will be imputed as 23:59.
- If the minutes are given, but not the hour, then the time will be regarded as completely missing and handled as above.
- If hours are given, but minutes are not, minutes will be imputed with 59.

8.6 Subgroups

The subgroup type of surgery (spinal and abdominal) is analyzed for the primary as well as for all secondary endpoints. Subgroups sex and race are analyzed for the primary endpoint.

Further subgroup analysis according to the predictive blood loss is planned for two secondary efficacy variables: total amount of transfusion products after IMP administration until end of surgery, total amount of RBC after IMP administration until end of surgery.

For specific adverse events and other safety parameters, subgroup analyses are being conducted based on type of surgery, sex and race. For more information, please refer to section 12.6.1.

8.7 Pooling of Centers

In case of low number of subjects per center, summaries of data by center would be unlikely to be informative. Therefore, data from all centers per country/region (if applicable) and in total will be pooled prior to analysis. Only enrollment will be summarized by country and center.

8.8 Completed Study

A subject is considered to have completed the study when he/she is presumed to have followed the CSP (i.e., completed visits approximately 5 weeks after surgery).

8.9 End of Surgery

End of surgery is defined as time of last suture.

8.10 Study Visits

The labels of study visits in this study are as following:

- Screening
- Baseline
- Surgery Day 1 (Prior 1st dose)
- Surgery Day 1 (Pre-dose)*
- Surgery Day 1 (15 min after IMP start)
- Surgery Day 1 (90 min after IMP start)
- Surgery Day 1 (End of Surgery)
- Day 2, Follow-up
- Day 3, Follow-up
- Day 5, Follow-up
- Day 8, Follow-up
- Closing Visit
- Early Discontinuation

*only applicable in case of repeated intra-operative IMP administration

For a subject who did not complete the study, date of early discontinuation is the last visit, when the subject discontinued from the study. As subjects are expected to attend a Closing Visit whether they complete or discontinue early from the study, subjects who complete the study will have their Closing Visit data summarized under 'Closing Visit', while subjects who discontinue early from the study will have their Closing Visit data summarized under 'Early Discontinuation'. If a subject terminates the study prematurely without having a closing visit, the data from the last regular visit will be summarized under this visit.

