## 4.4 Subjects Withdrawal Criteria and Replacements

The participation of an individual subject may be terminated prematurely for reasons such as:

- a. Withdrawal of written informed consent
- b. Study discontinuation due to subject's own request (e.g. personal reasons)
- c. Required treatment with any medication known or suspected to interfere with the IMP
- d. Life threatening thrombosis or TEE or life threatening hypersensitivity or any AE, laboratory abnormality, or other medical condition or situation occurs suggesting that continued participation in the study would not be in the best interest of the subject.
- e. Protocol deviation requiring discontinuation of study treatment
- f. Evidence of exclusion criteria or inclusion criteria not met
- g. Lack of study compliance
- h. Recommendation of the Data Safety Monitoring Board (DSMB)

A subject is entitled to discontinue participation in the clinical study at their own request at any time without stating a reason.

The investigator can terminate a subject's participation in the study at any time if continuation could lead to disadvantages for the subject which cannot be justified by the investigator.

The reason for withdrawal of the subject must be documented by the investigator together with all data collected until the day of premature study termination including laboratory results and assessment of AE. All examinations foreseen for the subject's last study visit (closing visit) should be performed. Afterwards, the subject will be treated according to local standards at the discretion of the investigator.

In case a subject withdraws due to an AE or SAE please follow the instructions given in section 15 Appendix 2: Reporting Procedures of this protocol.

Withdrawn subjects will not be replaced.

For screening failures occurring during the screening period the following data need to be documented in eCRF only:

• Informed consent

- Demographic data
- In-/Exclusion criteria
- End of Study (day and reason)
- AE information

For intra-operative screening failures (not randomized subjects) the following data need to be documented in eCRF only:

- Informed consent
- Demographic data
- In-/Exclusion criteria
- Classification of type of planned PMP surgery (due to underlying cause of the condition, that is the location and extent of the original tumor, including the inability to achieve complete cytoreduction)
- Estimated blood loss
- FIBTEM A10 at Baseline
- Duration of surgery

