#### Virus Serology

The immunological status of viral infections will be assessed at screening and closing visits for HIV, HBV and HCV, section III, Flowchart of clinical study. The following tests will be performed in the **local laboratory**:

- **HIV** (anti HIV1 and anti HIV2)
- hepatitis B (total hepatitis B core antibody [anti HBc], hepatitis B surface antibody [anti HBs], hepatitis B surface antigen [HBsAg])
- hepatitis C (anti HCV)

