Subjects who were treated with the study medication but did not complete the study as per protocol, should receive all the examinations and investigations scheduled for the last study visit. The investigator should make all efforts to contact subjects lost to follow-up and document the attempts in the subject's source data.

9.3.5 Immediate Reporting by Investigator to Sponsor (also refer to Appendix 2: Reporting Procedures)

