12.6.6 Viral Status

A shift table from screening to closing visit for virus serology parameters (hepatitis B, hepatitis C and HIV) will be summarized by treatment and treatment arm using number and percentage of subjects.

Listings for viral status will be created respectively for the SAF.

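### By the SAP's own visit labels, an early discontinuer's only post-dose virus serology is left out of the only by-arm serology table

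*SAP*

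**What the plan says.** **Visit labels.** SAP 8.10 lists Closing Visit and Early Discontinuation as two separate visits. It starts from the premise "As subjects are expected to attend a Closing Visit whether they complete or discontinue early from the study", then divides the data. Completers' results stay under Closing Visit. For the others, the rule is that "subjects who discontinue early from the study will have their Closing Visit data summarized under 'Early Discontinuation".

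**Viral-status outputs.** SAP 12.6.6 plans one table, broken down by treatment and by arm: "A shift table from screening to closing visit for virus serology parameters (hepatitis B, hepatitis C and HIV) will be summarized". It mentions neither Early Discontinuation nor a last available value. The section adds: "Listings for viral status will be created respectively for the SAF".

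**When serology is taken.** Protocol 9.2.1.4 (Virus Serology) says: "The immunological status of viral infections will be assessed at screening and closing visits for HIV, HBV and HCV". The flowchart in SAP 6.0 shows the same two time points.

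**Subjects who leave early.** Protocol 4.4 says: "All examinations foreseen for the subject's last study visit (closing visit) should be performed". Protocol 9.3.4 says that treated subjects who do not complete the study "should receive all the examinations and investigations scheduled for the last study visit".

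**The concern.** Viral status is a named secondary safety endpoint (Protocol 9.2.3, SAP 5.1), and SAP 7.2.3 frames it as a change. Protocol 10.7 intends it to be summarised by arm in the safety set. The plan asks for a final serology sample from subjects who leave early, then gives that sample a visit label that the serology table does not use.

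These subjects are not a random subset of those treated. Protocol 4.4 lists adverse events among the withdrawal reasons, and Protocol 6.7 discontinues any subject whose blind is broken. Seroconversion is an outcome for which a single case matters, so a by-arm count that omits measured results can mislead even when few are omitted.

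**Working it through.** The plan states no figure on this point that could be reproduced. The check sets the sections side by side, with a simple scale calculation at the end.

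1. **Is there a post-dose sample?** Yes, by intent. Protocol 4.4 and 9.3.4 ask for the closing-visit examinations in subjects who leave early, and SAP 8.10 expects a closing visit of everyone.
2. **How many post-dose serology values does a discontinuer have?** At most one, because the schedule has only screening and closing.
3. **Which label does it carry?** Early Discontinuation, under SAP 8.10.
4. **Which label does the table use?** Closing visit, under SAP 12.6.6. A programmer who selects on the labels in 8.10 finds no post-dose value for this subject.
5. **What happens to the subject in the table?** SAP 12.0 sets the default that percentages use everyone in the population of interest, with missing values shown as their own category. SAP 12.6 makes that population the safety set, and 12.6.6 states no exception. The subject therefore stays in the denominator, classed as missing although a result exists.
6. **Does the same happen to other laboratory data?** No. SAP 12.6.3 runs its shift tables to every post-baseline visit, which can include Early Discontinuation. The gap is specific to serology.
7. **Where else would the result appear?** In the safety-set listing of SAP 12.6.6. A positive result reported as an adverse event could also reach the table for adverse events of special interest, but SAP 12.6.1 identifies suspected transmission by two preferred terms only. An event coded to any other term is not found there. If it had been ticked as being of special interest and was not thromboembolic, the search rule would place it under relevant bleeding complications.

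**Scale.** Inputs: about 220 randomised (SAP 6.2), and an assumed early-discontinuation rate d, because the documents give none. The 10% in SAP 6.2 is expected exclusion from the per-protocol set, a different quantity.

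Upper limit on subjects affected = 220 × d

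| Assumed d | 220 × d | Rounded |
|---|---|---|
| 1% | 2.2 | 2 |
| 2% | 4.4 | 4 |
| 5% | 11.0 | 11 |
| 10% | 22.0 | 22 |

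These are upper limits for each assumed rate. Deaths, losses to follow-up and consent withdrawals may leave no final sample, and SAP 8.10 itself provides for subjects who stop without a closing visit.

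**The case against.** The strongest defence is that the lower-case wording in SAP 12.6.6 means the visit attended, not the label. SAP 8.10 calls the discontinuers' results their closing-visit data, and with only two serology time points, screening to closing can be read as first to last. Nothing in the documents expressly excludes early-discontinuation serology. The table layouts are in a separate specification (SAP 3.0 and Appendix 1), which may already have an Early Discontinuation row.

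That reading is possible, but 8.10 exists to say where such data are summarised, and 12.6.6 is a summary. Two readings that give different counts in a safety table should be settled in the SAP. A specification outside these documents cannot be assumed to override 8.10.

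A second defence is that the result is not lost. This stands in part. A reader might infer that the result disappears from the viral-status endpoint, that the table's denominator shrinks, or that a seroconversion would be reported as zero. The documents do not support these inferences: the listing covers the whole safety set, SAP 12.0 keeps the subject in the denominator, and suspected transmission is tabulated separately as an event of special interest. Still, a listing gives no by-arm count, and the two-term search is not a dependable substitute for the serology table.

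A third defence is that samples taken early are less informative. Protocol 7.1 already accepts serology drawn on the day of hospital discharge as closing-visit data when the closing visit is a phone call. Early timing is therefore a reason to flag a sample, not to leave it out.

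**Conclusion.** The concern holds in a limited form. Following the labels in SAP 8.10, measured post-dose serology of treated early discontinuers has no place in the one by-arm table of SAP 12.6.6, and these subjects would be shown as missing. The effect is confined to that table. Non-inferiority, superiority, alpha and sample size are untouched.

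The number affected cannot be derived from the documents. The range of about 2 to 22 rests on an assumed discontinuation rate of 1% to 10% and on every discontinuer being sampled, so it is a ceiling within that assumption and not an estimate. The conclusion also assumes that the table is programmed from the 8.10 labels. If closing visit is taken to mean the visit attended, the gap closes, but the SAP does not say so. This is a minor point that is worth correcting because the correction is so small.

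**What to change.** In SAP 12.6.6, define the shift as running from screening to the last post-dose serology, whether it is labelled Closing Visit or Early Discontinuation. Show the number tested under each label in each arm, so that tested and untested subjects can be told apart. In the listing, flag early-discontinuation samples and give their study day.

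The cost is one sentence in the SAP and one programming condition, with no new data. The downside is small: some included samples will have been taken before Day 36 and allow less time for seroconversion, which the flag and study day make visible.

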8.11 Amount of Blood Loss

During surgery, the blood loss will be quantified by measuring the continuous bleeding mass with a blood suction unit (and/or a cell saver) and by calculation of the amount of blood from swabs, surgical cloths and compresses. For the primary endpoint, the amount of blood will be measured for the time between decision to treat and end of surgery.

Calculation of blood loss:

Blood loss (mL) = Volume of blood on swabs, surgical cloths and compresses (mL) + Volume of blood in the suction container (mL) + Total volume of blood loss from other sources (mL)

Volume of blood on swabs, surgical cloths and compresses (mL) = Weight of used/unused surgical cloths and compresses (g) - Weight of dry swabs, surgical cloths and compresses (g). 1 g weight represents 1mL volume of blood.

Volume of blood in the suction container (mL) = Total volume of fluid collected in suction container (mL) - Total volume of anticoagulant solution in blood suction container (mL)* - Total volume of irrigation solution (mL)

* Not applicable for abdominal surgery

Total volume of irrigation solution = Capacity of irrigation syringe (mL) * Number of times irrigation syringe used

Handling of missing data:

For the calculation of **Blood loss**, Volume of blood on swabs, surgical cloths and compresses and Volume of blood removed from the surgical field by the blood suction is required. If there is at least one missing value (see above for single items needed) the blood loss cannot be calculated, and the volume will be missing.

For the calculation of blood in the suction container: Total volume of anticoagulant solution in blood suction container is not applicable for abdominal surgery and will not be considered for the calculation.

For the calculation of Total volume of irrigation solution: If Capacity of irrigation syringe is missing and Number of times irrigation syringe used > 0 then volume is missing. If Capacity of irrigation syringe is provided and Number of times irrigation syringe used is missing, then volume is missing. If Capacity of irrigation syringe is missing and Number of times irrigation syringe used = 0 then volume is 0.

8.12 Correction of Fibrinogen Level

The fibrinogen level is assessed by FIBTEM A10 test, MCF and Clauss assay at the following visits: screening, prior surgery (baseline), Surgery Day 1 (Prior 1st dose), Surgery Day 1 (Predose)*, Surgery Day 1 (15 minutes after start of first IMP administration), Surgery Day 1 (90 minutes after start of first IMP administration), Surgery Day 1 (end of surgery), and Day 2, Follow-up Visit. (* only applicable in case of repeated intra-operative IMP administration).

Rate of fibrinogen restoring = fibrinogen level at a post-baseline visit / fibrinogen level at baseline*100

If the rate of fibrinogen restoring is \geq 95%, then the fibrinogen level is considered to be successfully corrected at that post-baseline visit for the subject.

The above rate will be calculated for the following visits: Surgery Day 1 (15 minutes after start of first IMP administration), Surgery Day 1 (90 minutes after start of first IMP administration), Surgery Day 1 (End of surgery), and Day 2, Follow-up.

The time to first successful correction of fibrinogen level is classified into the following categories: "Within 15 minutes after IMP start", "Greater than 15 and less than or equal to 90 minutes after IMP start", "Greater than 90 minutes after IMP start" and "Unsuccessful correction".

At every visit, the time point relative to the start time of IMP is calculated in minutes as Collection Time of sample minus Start Time of IMP. Any corrections <15 minutes after IMP start are not considered for classification.

The earliest time point, when the rate is \ge 95%, is the time to first successful correction of fibrinogen level and will be used to categorize the subjects into the respective categories.

Subjects with time to first successful fibrinogen correction on Follow-up Visit Day 2 will be assigned to the category "Greater than 90 minutes after IMP start". If the rate of fibrinogen restoring is < 95% at all the time points, correction of fibrinogen level is reported as "Unsuccessful correction".

A sensitivity analysis adds a time window of ±3 minutes to the category "Within 15 minutes after IMP start", so that time points ≥12 and ≤18 minutes fall into this category. To the category "Greater than 15 and less

than or equal to 90 minutes after IMP start" a time window of +3 minutes is added, so that time points between >18 and ≤93 minutes fall into this category. Corrections >93 minutes are categorized as "Greater than 90 minutes after IMP start".

In addition, and independent from the above categories, the time to first successful correction is classified into "Until end of surgery" or "Not within surgery". Subjects with time to first successful correction at the time point Surgery Day 1 (End of surgery) are assigned to "Until end of surgery". Subjects with time to first successful correction on Follow-up Visit Day 2 are assigned to "Not within surgery". For the visits Surgery Day 1 (15 minutes after start of first IMP administration) and Surgery Day 1 (90 minutes after start of first IMP administration) and Surgery and subjects are assigned to "Until end of surgery" or "Not within surgery" accordingly. If the rate of fibrinogen restoring is < 95% at all the time points, correction of fibrinogen level is reported as "Unsuccessful correction".

The whole analysis for the correction of fibrinogen levels is also done based on results obtained from MCF and Clauss assay to perform sensitivity analyses.

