#### Repeated IMP Administration

According to the study design and the described treatment algorithm BT524 or cryoprecipitate will be administered pre-emptively as the primary hemostatic therapy if clinical judgement approximately 60 minutes after the start of cytoreductive PMP surgery predicts a clinically relevant bleeding of > 2 L intra-operatively, requiring hemostatic treatment during surgery.

Repeated intra-operative administration of IMP is possible depending on the subjects' clinical condition and their individual FIBTEM A10 results (Figure 3).

If bleeding continued after completion of IMP administration, and further IMP treatment is not advisable a **transfusion protocol according to local standards** (standard of care) should be followed.

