### 6.2 Dosage and Administration

The first IMP (BT524 or cryoprecipitate) dose will be administered pre-emptively, based on clinical judgement (prediction of clinically relevant bleeding of more than 2 L, requiring hemostatic treatment during surgery).

Further IMP administration depends on the extent of bleeding and the subject's clinical condition, and will be guided by FIBTEM A10 results. Therefore, the functional fibrinogen level should be determined intra-operatively on an individual subject basis by FIBTEM thromboelastometry prior to IMP administration.

A FIBTEM A10 < 12 mm may trigger the administration of IMP in case a further clinically relevant bleeding occurs. Nevertheless, IMP may be administered prior to the determination of FIBTEM A10 in a subject who is bleeding if deemed appropriate as per current clinical standards (that is suspected acquired hypofibrinogenaemia with rapid bleeding precluding waiting for laboratory results).

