#### 9.1.3.2 Specification of Secondary Efficacy Endpoints

• Proportion (%) of subjects with successful correction of fibrinogen level 15 minutes after start of first IMP administration.

Successful correction of fibrinogen level in a subject is defined as restoring fibrinogen FIBTEM A10 baseline level to at least 95% measured by ROTEM 15 minutes after start of first IMP administration. A correction of at least 95% is considered successful, as measurement methods has a coefficient of variation of about 5% (Solomon et al., 2015).

- Time to first successful correction of fibrinogen level (15 minutes or 90 minutes after start of first IMP administration, end of surgery, not within surgery).
- Total amount of transfusion products (allogenic blood products) or autologous blood transfusion infused after start of first IMP administration until end of surgery. The end of surgery is defined as time of last suture.

- Amount of RBCs (allogenic and autologous) infused after start of first IMP administration until end of surgery. The end of surgery is defined as time of last suture.
- Post-operative blood loss in the first 24 hours.
- Proportion (%) of subjects with rebleeds. Rebleeds are defined as any bleed requiring hemostatic treatment (including reoperation) after the end of surgery until Day 8.
- Hospital length of stay after surgery, defined as the date of discharge minus the date of surgery.
- In-hospital mortality.

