8.2 Baseline

If not stated otherwise, the last non-missing valid observation prior to surgery will serve as the baseline measurement.

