12.5.3.1 Correction of Fibrinogen Level

The proportion (%) of subjects with a successful correction of fibrinogen level (by FIBTEM A10) 15 minutes after start of first IMP administration will be compared between the treatment arms using a Cochran-Mantel-Haenszel (CMH) approach stratified by predictive blood loss (> 1,000 mL to \leq 2,000 mL and > 2,000 mL). The number and percentage of subjects with a successful correction of fibrinogen level 15 minutes after start of first IMP administration will be presented for both treatment arms with corresponding 95% confidence intervals. The estimated treatment effect (i.e., the difference in response rate between the treatment arms, BT524 – FFP/cryoprecipitate), corresponding 95% confidence interval, and 2-sided p-value for the difference will be presented.

The time to first successful correction of fibrinogen level (by FIBTEM A10) is assigned to the following categories: "Within 15 minutes after IMP start", "Greater than 15 and less than or equal to 90 minutes after IMP start", "Greater than 90 minutes after IMP start" and "Unsuccessful correction". The 4 categories will be compared between the two treatment arms using a Chi-square test.

In an additional analysis the time to first successful correction of fibrinogen level (by FIBTEM A10) is classified relative to the end of surgery into "Until end of surgery", "Not within surgery" or "Unsuccessful correction". The 3 categories will be compared between the two treatment arms using a Chi-square test.

For the above Chi-square tests, the number and percentage of subjects in each category will be presented for each treatment arm, together with an overall p-value for the difference between the two treatment arms.

The absolute values and change from baseline in fibrinogen levels by FIBTEM A10, together with the rate of fibrinogen restoring will be summarized with descriptive statistics over time by treatment arm. The absolute values at screening and change from screening at baseline will also be summarized for fibrinogen levels by FIBTEM A10.

In addition, the test results of MCF and Clauss assay will be summarized in the same way. The results of these three assays will be listed for the All Subjects Enrolled Set.

Mean with SD, median with interquartile ranges will be presented graphically over time for both treatment arms for FIBTEM A10, MCF and Clauss assay.

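### Successful correction of fibrinogen does not require a deficit before dosing, so subjects with nothing to correct can be counted as corrected

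*SAP*

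**What the plan says.** Protocol 9.1.3.2, repeated in SAP 7.2.1, defines success as "restoring fibrinogen FIBTEM A10 baseline level to at least 95% measured by ROTEM 15 minutes after start of first IMP administration". SAP 8.12 makes this operational: "Rate of fibrinogen restoring = fibrinogen level at a post-baseline visit / fibrinogen level at baseline*100". If the result is 95% or more, "then the fibrinogen level is considered to be successfully corrected at that post-baseline visit for the subject". Under SAP 8.2, "the last non-missing valid observation prior to surgery will serve as the baseline measurement".

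FIBTEM A10, MCF and Clauss are also measured at the prior-first-dose visit, but SAP 8.12 calculates the restoring rate only at 15 minutes, 90 minutes, end of surgery and Day 2.

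On dosing, Protocol 6.2 states: "The first IMP (BT524 or cryoprecipitate) dose will be administered pre-emptively, based on clinical judgement". The Protocol's account of repeated IMP administration says the IMP "will be administered pre-emptively as the primary hemostatic therapy if clinical judgement approximately 60 minutes after the start of cytoreductive PMP surgery" predicts more than 2 L of bleeding. FIBTEM A10 below 12 mm is mentioned for further doses only. The spinal inclusion criterion (SAP 6.1) is bleeding of about 1 L, again without a fibrinogen threshold.

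SAP 12.5.3.1 compares the 15-minute success proportion by a CMH method, with a difference, confidence interval and p-value, and compares the time-to-first-correction categories by chi-square. SAP 12.5.3 uses the FAS, overall and by surgery type. The MCF and Clauss sensitivity analyses follow the same rule.

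**The concern.** Restoring and correcting presuppose that something was lost. The rule checks only where the level ends up, not whether it had fallen. A subject who never dropped below 95% of the pre-surgery value can be recorded as corrected at the first time point at which the rule is applied.

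The secondary objective is to show efficacy partly through intra-operative correction of fibrinogen. If many subjects have no deficit when dosed, the success proportion describes a mixture of correction and absence of need, and the reader cannot tell the two apart. The comparison between arms may be distorted as well. The share without a deficit may also differ between pre-emptively treated PMP subjects and spinal subjects treated after actual bleeding.

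**Working it through.** **The plan's own figures.** The only sample-size calculation is for the primary endpoint. With SD 375 mL, margin 150 mL, one-sided 2.5% and 80% power, n = 2 × (1.960 + 0.842)² × (375/150)² ≈ 98.1, so 99 per arm; an exact t calculation at 100 per arm gives 80.4% power. The stated 100 per arm is reproduced. No expected rate, difference or power is given for fibrinogen correction, so what follows rests on assumptions.

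**Can a subject with no deficit score as a success?**

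- *No treatment effect at all.* SAP 7.2.1 gives an assay CV of about 5%. Take both readings as lognormal with that CV and the true level as unchanged. The log ratio then has SD √2 × √ln(1.0025) = 0.0707, and P(ratio ≥ 0.95) = Φ(0.0513/0.0707) ≈ 77%. If only one reading carries error it is about 85%.
- *Some treatment effect.* Protocol 6.2 expects about 1 g/L from a cryoprecipitate dose infused over roughly 30 minutes. Take half of that at 15 minutes and ignore continuing loss. A subject at exactly 95% before dosing reaches (0.95 × 2.0 + 0.5)/2.0 = 120% for a baseline of 2.0 g/L, and (0.95 × 4.5 + 0.5)/4.5 = 106% for 4.5 g/L (the normal range in Protocol section 1). This is on the concentration scale, so for FIBTEM A10 it is only a guide.

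**Effect on the rates.** Let q be the share at 95% or more before dosing, p1 and p2 the success rates among subjects with a deficit, and s1 and s2 those among subjects without one (1 = BT524, 2 = comparator).

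- Observed rate = q·s + (1 − q)·p, which exceeds p whenever s > p.
- Observed difference = q(s1 − s2) + (1 − q)(p1 − p2).

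Assume p1 = 80%, p2 = 60%, s1 = s2 = 100% and 100 per arm. Power is two-sided 5%, by the normal approximation for two proportions.

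| q | BT524 | Comparator | Difference (points) | Power, all subjects | Power, deficit only (n per arm) |
|---|---|---|---|---|---|
| 0% | 80% | 60% | 20 | 87.6% | 87.6% (100) |
| 10% | 82% | 64% | 18 | 82.3% | 83.9% (90) |
| 20% | 84% | 68% | 16 | 75.9% | 79.4% (80) |
| 30% | 86% | 72% | 14 | 68.4% | 73.8% (70) |
| 50% | 90% | 80% | 10 | 50.8% | 59.0% (50) |

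**Dependence on equal success.** Hold q = 30% and s1 = 100%. The difference is 0.30 × (1 − s2) + 0.70 × 0.20. For s2 = 100%, 90%, 80% and 70% it is 14, 17, 20 and 23 points. The dilution disappears at s2 = 80% and reverses below that.

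**The case against.** A reader might infer that the rule necessarily shrinks the arm difference. The documents do not support that. According to the Protocol, a 1 g syringe of BT524 can be given in under 20 seconds, while two pools of cryoprecipitate take about 30 minutes. FFP is described as relatively low in fibrinogen and needing large volumes. A subject near baseline who goes on bleeding might stay above 95% on one product and not on the other. Holding the level up after pre-emptive dosing can itself be a product effect. This stands, so only the overstatement of correction is near-certain once q exceeds zero.

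A reader might also infer that spinal subjects are dosed without reference to fibrinogen. Only their inclusion criterion is visible here. Protocol section 2 says that spinal treatment is not described in this country version, so their first-dosing rule cannot be judged.

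Part of the information is already planned: FIBTEM A10, MCF and Clauss are summarised over time by arm and listed, and the analysis is repeated by surgery type. Summaries over time do not split the success proportion by pre-dose status, so the gap remains.

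The strongest objection is to making the deficit-only subset the main test. Protocol 10.6 assigns secondary efficacy analyses to the FAS. In addition, the prior-first-dose sample is not timed relative to randomisation, and cryoprecipitate is thawed only after allocation. If the sample is drawn after allocation, a longer wait in one arm could place more of its subjects in the subset. This stands too. The subset therefore belongs in a supplementary analysis.

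**Conclusion.** The gap is certain from the text: success needs no deficit before dosing, and nothing else in the plan separates subjects who had one from those who did not. The correction rates are overstated, as a measure of correction, to the extent that subjects without a deficit succeed more often than the rest.

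The size is unknown because q is not in the documents. In the illustration above, q = 20% raises the rates by 4 and 8 points and cuts the difference from 20 to 16. That rests on the assumed 80% and 60% and on equal success without a deficit. With unequal success the difference may be unchanged or larger.

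It would be wrong to read this as a threat to the trial's conclusion. SAP 12.5.2 calls the secondary analyses exploratory, and the primary endpoint and sample size are untouched. It is a cheap improvement to the interpretation of a secondary endpoint.

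**What to change.** Keep the protocol-defined FAS analysis as the main analysis. Then, before database lock:

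1. In SAP 8.12, also compute the restoring rate at the prior-first-dose visit.
2. In SAP 12.5.3.1, pre-specify a table of success by pre-dose status (below 95%, or 95% and above), arm and surgery type.
3. Pre-specify a supplementary CMH comparison and the time-to-correction tables in subjects with a pre-dose rate below 95%.
4. Repeat items 2 and 3 for MCF and Clauss.
5. Report pre-dose status by arm and the sample time relative to randomisation, so that any imbalance in the subset can be seen.

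The cost is one derived variable from samples already taken and a few extra tables. The supplementary denominators are smaller, and an assay CV of about 5% will misclassify some subjects: on the error model above, a true 90% reads as 95% or more about 22% of the time.
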